7.5 Measurements of Treatment Compliance

Percentage compliance in the double-blind Treatment Period will be derived as:

$(\text{Number of actual tablets taken}) * 100 / \text{Number of tablets expected to be taken}$

Where actual tablets taken will be defined as the total number of tablets dispensed minus the total number of tablets returned during the double-blind Treatment Period. The number of tablets expected to be taken will be defined as the number of days within the double-blind Treatment Period.

Percentage compliance will be summarized descriptively by treatment group and overall for the Safety population.

The number and percentage of compliant patients will be presented by treatment group and overall for the Safety population, where compliant is defined as percentage compliance between 80.0% and 100.0% inclusive. The following percentage compliance categories will also be presented:

- <80.0%
- 80.0-100.0%
- >100.0%

7.6 Efficacy

The 6-week double-blind Treatment Period will provide the main dataset for inferential analyses.

All efficacy analyses will be performed on the mITT population. Supportive, exploratory analyses will be performed on the PP population.

Testing among the secondary endpoints will not be adjusted for multiplicity, and hence, the analyses will be exploratory. Other endpoints will likewise not be adjusted for multiple testing. Unadjusted p-values will be presented for all analysis results.

7.6.1 Primary Efficacy Analysis

The primary endpoint is the change from Baseline to Week 6 in ADPS, based on Question 5 of the ZBPI, the 11-point numerical rating scale (0 [No Pain] to 10 [Pain as bad as you can imagine]). The primary analysis will be based on observed data including data measured after the initiation of rescue medications.

Baseline is defined as the average of the Week 2 Run-in Period data collected by patients in the daily pain diary, provided that ≥ 5 days from that period are available for analysis. The post-Baseline values will be calculated by week as the mean value of the Question 5 for ADPS of the ZBPI, rated by patients each evening and collected during the target week period. A minimum of 4 non-missing data within the target week period is required for the calculation. The change from

Baseline values at post-Baseline weeks will be calculated as the absolute difference between the Baseline value and post-Baseline values, i.e.

$$\text{change from Baseline} = \text{post-Baseline value} - \text{Baseline value}$$

The ADPS calculated for each post-Baseline week until Week 6, and the change from Baseline in ADPS at post-Baseline weeks until Week 6 will be summarized by Week using standard descriptive statistics. Data from all study visits, scheduled and unscheduled, and from the daily pain diary will be listed.

A restricted maximum likelihood-based, MMRM approach will be used to assess the difference between LX9211 and placebo in the primary endpoint (ie, change from Baseline to Week 6 in the ADPS derived from data collected daily from Question 5 of the ZBPI instrument). The MMRM model will include fixed effects of treatment, week, treatment-by-week interaction, the randomization stratum of Baseline pain severity (moderate, severe), and the Baseline ADPS score as a covariate. An unstructured covariance structure will be used to model the within-patient error. The Kenward-Roger approximation will be used to estimate the denominator degrees of freedom. Other covariance structures will be explored should convergence not be met.

The adjusted mean change in ADPS from Baseline to Week 6 for each treatment group and the 95% confidence intervals (CIs) will be estimated in the framework of this model, as well as the between-group differences (comparing LX9211 to placebo) and the 95% CIs for the difference.

Summarization of the inferential statistics will include the Least Squares means (LS means), standard error (SE) of the estimates, p-values, and 2-sided 95% CIs. These statistics will be provided for the within treatment group changes from Baseline and for the comparison of LX9211 versus placebo for the change from Baseline scores. Tabulation of the inferential results (CIs and p-values) will include the observed findings from the statistical model.

The same analysis will be performed using the PP population.

Figures displaying the arithmetic mean change from Baseline in ADPS by weeks as well as LS mean change by weeks, including Week 6, will be presented by treatment group for the mITT population.

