10.4.2.1 Analysis of Primary Efficacy Endpoint

The primary endpoint is the change from Baseline to Week 6 in ADPS. The primary analysis will be based on observed data including data measured after the initiation of rescue medications. Baseline is defined as the average of the Week 2 Run-in period data, provide that ≥ 5 days from that period are available for analysis. The Week 6 mean value will be derived from the 7-day period immediate to the endpoint, provided that ≥ 4 days of non-missing data are collected.

A restricted maximum likelihood-based, mixed-effects model repeated measures (MMRM) approach will be used to assess the difference between LX9211 and placebo in the primary endpoint (ie, change from Baseline to Week 6 in the ADPS derived from data collected daily from Question 5 of the ZBPI instrument). The MMRM model will include fixed effects of treatment, week, treatment-by-week interaction, the randomization stratum of Baseline pain severity, and the Baseline score as covariate. An unstructured covariance structure will be used to model the within-patient error. The Kenward-Roger approximation will be used to estimate the denominator degrees of freedom. Other covariance structures will be explored should convergence not be met. In the event that a rescue medication is used, a supplementary MMRM model will be applied to a dataset that excludes data collected after the initiation of the rescue medication. To assess the robustness of the MMRM analyses performed under the missing at random (MAR) assumption, and given the long half-life of LX9211, pattern mixture models (PMM) with copy reference-based imputation methods will be applied to both datasets (with and

without data collected after the initiation of the rescue medication). The imputed datasets will be combined by use of Rubin's rule and analyzed using an analysis of covariance (ANCOVA) model fitted for the fixed effects of treatment, the randomization stratum of Baseline pain severity, and the continuous fixed covariate of Baseline score.

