2.3 Sample Size and Power

The proposed sample size is derived by satisfying the original design assumptions made for the primary efficacy endpoint. It is assumed that the difference in treatment group means is 0 under the null hypothesis (H_0) and is unequal to 0 under the alternative hypothesis (H_1); a 2-sided hypothesis under test. Under the H_1 , the difference in group means of LX9211 minus placebo is expected to be -0.8 units with a common standard deviation (SD) of 1.0 units. These assumptions yield an effect size of 0.8. The effect size is the absolute value of the difference in treatment group means divided by the common SD of that difference. A uniform dropout rate of 0.15 is anticipated, and adjustment of the effect size for this rate results in an estimate 0.68; the adjusted difference in group means is equal to -0.8 units x 0.85 = -0.68. For a 2-sided test sized at $\alpha = 0.05$, 37 patients per treatment group are required under a 1:1 randomization ratio to detect the stated treatment difference under H_1 with statistical power equal to 82.27% under a single stage design. The total planned N = 74 patients.

This study is designed as a group sequential trial with 1 interim look at the 50% information time point and a final analysis at 100%. A non-binding futility boundary will be used to test for futility of the primary endpoint. The futility boundary is 1-

sided with $\alpha = 0.025$ and for the parameters specified, a power estimate of 82.53% is derived.

Sample Size Reestimation

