7.1 General Principles

All data processing, summarization and analyses will be performed using Hosted SAS Environment / Version 9.4 (or later) of the SAS® (SAS Institute, Cary, NC) statistical software package.

The following principles will be applied to all tables, figures, and listings (TFLs) unless otherwise stated:

Principle	Value
Significant tests	2-sided and use a 5% significance level for the main effect of study treatment
Treatment group labels and order presented	LX9211 200 mg/20 mg Placebo Total (if applicable)
Tables	Data in summary tables presented by treatment group, assessment (where applicable) and visit (where applicable)
Listings	All data collected presented by treatment group, site, patient, and visit (where applicable), date, unless otherwise specified

Statistical Analysis Plan Final v3.0

Lexicon Pharmaceuticals, Inc.
Protocol ID: LX9211.1.202-PHN

Labcorp Study ID: [REDACTED]

Principle	Value
Descriptive summary statistics for continuous variables	Number of patients/observations with non-missing data (n), mean, standard deviation (SD), median, minimum and maximum. If n=0 then other statistics will be blank.
Descriptive summary statistics for categorical variables	Frequency counts and associated percentages [n (%)] presented to 1 decimal place.
Denominator for percentages	Number of patients per treatment group in the analysis population, unless stated otherwise in table shell(s)
Include "Missing" as category	Yes, when the number missing is greater than 0 for at least 1 treatment group
Display for 0 percentages	Leave Blank
Display for treatment compliance and percentage change from Baseline	Present Mean and Median to 1 decimal place and SD to 2 decimal places
Display to 1 more decimal place than collected value	Mean Mean Difference Median Confidence Interval
Display to 2 more decimal places than collected value	SD Standard Error
Display for p-values	x.xx for p-value >0.05 x.xxx for p-value ≤ 0.05 and ≥0.001 <0.001 for p-value <0.001
Limit of precision for displays	3 decimal places
Date Format	DDMMYYYY
Display for analysis not done	NC (not calculated), NA (not applicable), ND (not done), or NR (not reported). Refer to table shells.

For continuous efficacy variables that are derived as percentage change from Baseline outcomes, the applied analyses and their results will be used for descriptive purposes.

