7.6.3 Sensitivity Analyses

In the event that rescue medication is used, a supplementary MMRM model will be applied to the primary endpoint dataset that excludes data collected after the initiation of the rescue medication using the mITT population. This model will be parameterized in the same manner as will be used for the primary analysis of this endpoint.

In addition, to assess the robustness of the MMRM analyses performed under the MAR assumption, and given the long half-life of LX9211, PMMs with copy reference-based imputation methods will be applied to both datasets (with and without data collected after the initiation of the rescue medication) using the mITT population. Methods will be adopted to estimate for both non-monotone and monotone missing data patterns. Imputations for the non-monotone missing data pattern will be the initial step. The imputation algorithm based on Monte Carlo Markov Chain methodology will be used assuming a MAR mechanism for the missing data; 100 imputations will be used. Then multiple imputations will be performed to assign the response variable at consecutive study weeks in a sequential manner for the monotone missing data pattern. For this chain-based method, control-based imputation will be applied so that there is no direct use of observed data from the LX9211 treatment group in estimating the imputation model. The method is derived such that it builds its imputation only on the placebo group data. The imputed datasets will be combined by use of Rubin's rule and analyzed using an analysis of covariance (ANCOVA) model fitted with the fixed effects of treatment, the

randomization stratum of the Baseline pain severity (moderate, severe), and the continuous fixed covariate of Baseline score. The ANCOVA analysis will be performed at Week 6 only. Summary statistics from applying the ANCOVA model across the multiple imputed datasets will be combined to obtain an overall estimate of the treatment group differences.

Another sensitivity analysis will be performed for the weekly sleep score, which is the average of the daily score by week through Week 6. The baseline is the Week 2 sleep score from the Run-in period. The change from baseline to Week 6 will be analyzed by using a similar MMRM method as the primary endpoint.

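### The primary MMRM imposes one Baseline slope and one stratum effect on all six weeks; if the Baseline relation weakens over time, the Week 6 contrast loses some precision, and adding covariate-by-week terms is a cheap safeguard

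*SAP*

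**What the plan says.** SAP 7.6.1 lists the fixed effects as treatment, week, "treatment-by-week interaction, the randomization stratum of Baseline pain severity (moderate, severe), and the Baseline ADPS score as a covariate". Protocol 10.4.2.1 has the same list, ending in "the randomization stratum of Baseline pain severity, and the Baseline score as covariate", and the Protocol synopsis agrees. Neither Baseline nor stratum is crossed with week.

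The outcome is "The ADPS calculated for each post-Baseline week until Week 6", expressed as change from Baseline, so six weekly values enter the model. On the covariance, "An unstructured covariance structure will be used to model the within-patient error". Tests are "2-sided and use a 5% significance level for the main effect of study treatment".

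SAP 6.2.2 names the pattern-mixture analysis as the primary sensitivity analysis. According to SAP 7.6.3, its imputed datasets go into an ANCOVA with treatment, stratum and Baseline: "The ANCOVA analysis will be performed at Week 6 only". That ANCOVA therefore estimates a Baseline slope specific to Week 6. No planned MMRM does. The sleep and ZBPI 9A-G models (SAP 7.6.2.1 and 7.6.2.4) and the subgroup models (7.6.4) follow the primary form.

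**The concern.** In a model for change with main effects only, the relation between Baseline ADPS and change must be the same at Week 1 as at Week 6. In longitudinal scores the Baseline value often predicts later values less well. If that happens here, the single slope is a weighted average of the weekly slopes and need not suit Week 6. The misfit goes into the Week 6 residual variance and widens the interval for the trial's one primary test.

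There is a second, smaller consequence. The reference-based analysis is meant to show what the missing-at-random assumption contributes. If the two analyses also adjust for Baseline differently, part of any gap between them in this one trial may come from the covariate model instead.

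**Working it through.** **1. The plan's own figure.** Inputs from SAP 2.3: the difference is "expected to be -0.8 units with a common standard deviation (SD) of 1.0 units", a 15% dropout rate shrinks it to 0.8 × 0.85 = 0.68, and "37 patients per treatment group are required under a 1:1 randomization ratio". The noncentrality is (0.68/1.0) × √(37/2) = 2.92. A two-sample t test with 72 df gives power of 82.27%, which reproduces the plan. The normal approximation gives 83.27%.

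**2. Assumptions not in the documents.** Baseline SD and every weekly SD are 1. The Baseline correlation ρ falls linearly from Week 1 to Week 6. Residual correlation is 0.8 per week of lag. The weekly slope of score on Baseline is then ρ, and the residual variance is 1 − ρ². A falling ρ therefore both moves the slope and raises the later residual variance. A Week 6 correlation of 0.50 gives a change SD of √(2 − 2 × 0.50) = 1.0, as planned.

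**3. Formula.** The common slope is c = Σ wₜρₜ with weights w = S⁻¹1/(1′S⁻¹1), where S is the residual covariance including the misfit (solved by iteration). The Week 6 variance inflation is 1 + (ρ₆ − c)²/(1 − ρ₆²). For 0.85 to 0.50: c = 0.787, so 1 + 0.287²/0.75 = 1.11.

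**4. Results.** Power is by-week slope versus common slope, from the noncentral t with the Week 6 residual SD. The last column uses 37 × 0.85 = 31.45 per arm.

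| ρ, Week 1 to Week 6 | Weight on Week 1 / Week 6 | c | Variance inflation | Power: 0.68, 37 per arm | Power: 0.8, 15% loss |
|---|---|---|---|---|---|
| 0.80 to 0.80 | 0.36 / 0.36 | 0.800 | none | 99.8 vs 99.8% | 99.9 vs 99.9% |
| 0.80 to 0.70 | 0.49 / 0.26 | 0.762 | about 1% | 98.1 vs 98.1% | 99.2 vs 99.2% |
| 0.80 to 0.60 | 0.60 / 0.21 | 0.738 | 3% | 95.0 vs 94.5% | 97.4 vs 97.0% |
| 0.85 to 0.50 | 0.83 / 0.15 | 0.787 | 11% | 91.5 vs 88.5% | 95.0 vs 92.8% |
| 0.90 to 0.50 | 1.04 / 0.10 | 0.867 | 18% | 91.5 vs 86.6% | 95.0 vs 91.3% |

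Only the last two rows match the planned change SD of 1.0. The milder rows imply a smaller SD, so read their inflation rather than their power level. Other residual structures give more inflation in the last three rows: 4, 17 and 26% with 0.9 per week of lag, and 6, 23 and 34% with exchangeable correlation 0.7.

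**5. Simulation with both interactions.** This used 74 patients, stratified blocks, 15% random dropout, a true effect of −0.8, Baseline SD about 1.1, 1,100 trials per scenario, and a t reference with 58 df in place of Kenward-Roger. Power is written model versus model with both covariate-by-week terms. The first figure in each pair is for residual correlation 0.9 per week of lag, the second for exchangeable 0.7. Slopes are of change on Baseline.

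- Constant −0.25: 93.5 vs 92.8%; 93.8 vs 93.2%. SE ratio (written/by-week) 0.995.
- −0.1 to −0.3: 91.9 vs 92.0%; 92.3 vs 92.6%. SE ratio 1.02.
- −0.1 to −0.4: 93.9 vs 95.5%; 91.5 vs 95.0%. SE ratio 1.05 and 1.06.
- 0 to −0.5 (extreme): 92.4 vs 97.1%; 91.4 vs 97.6%. SE ratio 1.16 and 1.20.

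Mean estimates stayed at about −0.80 in both models throughout.

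**6. The sensitivity comparison.** A chance Baseline difference δ between arms shifts the common-slope estimate against the Week 6-slope estimate by (c − ρ₆)δ. For 0.85 to 0.50, one SD of δ without stratification is √(2/37) = 0.23, so the shift is about 0.287 × 0.23 = 0.07 units in either direction. Stratification makes it smaller.

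**The case against.** The strongest reply is that nothing in the documents shows a drifting slope. This stands: they give no weekly slopes, variances or correlations. A reader might infer that the written model certainly loses precision, but with a constant slope it is slightly more precise.

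A reader might also infer that the early weeks always dominate the common slope. That requires residual variance that grows over time. With flat residual variance, Weeks 1 and 6 carry equal weight (0.36 to 0.42 each under autoregressive correlation, 0.17 for every week if exchangeable). Growth does follow from a weakening Baseline relation if the total SD is constant, but that too is an assumption.

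It is also tempting to apply the inflation to 82.27% and report about 78% or 76% for the strong-drift rows. The planned SD of 1.0 is for unadjusted change, so 82.27% counts on no gain from covariates. In every row of the table the written model stays above it. Nor is the trial fixed at 74 patients, since the re-estimation may raise the number to 148.

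Finally, there is no validity problem. The contrast is unbiased, randomization is stratified by pain severity, and the covariate-form difference adds no expected gap to the sensitivity comparison. All of this stands. It limits the point to precision and to a cleaner comparison, but it does not argue for keeping the restriction.

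**Conclusion.** The point holds in conditional form. The plan imposes a common Baseline slope and a common stratum effect on Weeks 1 to 6, and gives no reason for doing so. If the Baseline relation weakens over the weeks, the Week 6 variance rises by about 1% (correlation 0.80 to 0.70), 3% (0.80 to 0.60) or 11 to 18% (0.85 or 0.90 to 0.50), given residual correlation 0.8 per week of lag. At the planned effect that is about 0 to 5 power points; the most extreme simulated drift, under another correlation structure, reached about 6. There is no bias, and the stated power is not in error. The mismatch with the Week 6-only ANCOVA is real but not systematic. This is an inexpensive improvement, not a defect that threatens the conclusion.

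**What to change.** Before unblinding, and decided by staff who have not seen treatment-level results, add Baseline ADPS-by-week and stratum-by-week interactions to the primary MMRM in SAP 7.6.1, Protocol 10.4.2.1 and the synopsis. Keep the Week 6 LS-mean difference as the primary contrast. Make the matching change in the full-sample MMRMs that copy the model: 7.6.2.1 by week, and 7.6.2.4 by visit with that item's own Baseline. In the smaller subgroup MMRMs (7.6.4), use Baseline-by-week only where the model converges, and no stratum term in the severity subgroup, as already planned.

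The cost is one line of wording and code, no new data, and 10 fixed-effect degrees of freedom in the primary model (5 for each interaction). If the slope is in fact constant, the standard error rises by about 0.5% and power falls by less than 1 point. Stratum and Baseline overlap, since both come from the run-in diary, so most of any gain should come from the Baseline term. If the sponsor prefers the present model, the SAP should say why a constant slope is expected.

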7.6.2 Secondary Efficacy Analysis

Analysis of the secondary efficacy endpoints will be based on the mITT population. Descriptive statistics for all the secondary efficacy endpoints will be presented by treatment group and by study visit/week where appropriate. Data from all study visits, scheduled and unscheduled, and from the daily pain diary will be listed. Post-Baseline data through Week 6 will be used in the analyses where inferential statistics are presented, including observations occurring after discontinuation of

study drug. Figures displaying mean change from Baseline, LS mean change at Week 6, and bar charts displaying proportions, will be presented by treatment group.

Continuous secondary efficacy endpoints: ZBPI scores, measured at multiple time points, will be analyzed using a similar modeling strategy as for the primary endpoint.

The ordinal secondary endpoint, PGIC response at Week 6, will be analyzed using an analysis of variance (ANOVA) model to test and estimate the treatment effect.

Categorical secondary endpoints: the proportion of responders based on the 11-point numerical rating scale (NRS) and the proportion of patients discontinuing study treatment due to lack of efficacy will be compared between treatments using a Cochran-Mantel-Haenszel (CMH) test stratified by the randomization factor of Baseline pain severity (moderate, severe). Patients with missing measurement at Week 6 will be considered non-responders. In general, a non-responder imputation (NRI) rule will be applied to assign outcomes to all study weeks with missing observations.

The Kaplan-Meier (KM) method will be used to generate statistical summaries of the time to loss of efficacy variable among patients who achieve $\geq 30\%$ reduction in ADPS based on Question 5 of the ZBPI from Week 6 to Week 11.

The qualitative patient interview substudy will be managed by a separate vendor (RTI-Health Solutions, Research Triangle Park, NC). The data analysis methods they employ will be detailed in a separate statistical analysis plan and the results will be reported separately by them.

7.6.2.1 Change from Baseline to Week 6 in pain interfering with sleep based on Question 9F of the ZBPI

The change from Baseline to Week 6 in pain interference with sleep based on Question 9F of the ZBPI "Indicate the one number that describes how, in the past 24-hours shingles pain has interfered with your: Sleep (0 [Does not interfere] to 10 [Completely interferes])", rated by patients and collected each evening in the daily pain diary will be summarized using standard descriptive statistics and the treatment effect will be evaluated using a similar MMRM method as specified for the primary efficacy analysis of change from Baseline to Week 6 in ADPS.

In this case, the Baseline value for the interference with sleep using Question 9F of the ZBPI is defined as the value collected at the time of the clinic visit on Day 1. The post-Baseline values will be calculated by week as the mean value of the Question 9F of the ZBPI, rated by patients each evening and collected during the acceptable week period. A minimum of 4 non-missing data within the target week period is required for the calculation.

7.6.2.2 Proportion of patients with $\geq 30\%$ reduction in pain intensity in ADPS based on Question 5 of ZBPI from Baseline to Week 6

Baseline and Week 6 ADPS scores will be based on the same mean values as derived for the primary endpoint. The frequency and percentage of patients with $\geq 30\%$ reduction in pain intensity from Baseline at Week 6 will be presented by treatment group. Response/Non-response categories will be defined as:

- If % change from Baseline $\leq (-30) \rightarrow$ Response
- If missing % change from Baseline or $> (-30) \rightarrow$ Non-response

Where % change from Baseline = $100 * (\text{post-Baseline value} - \text{Baseline value}) / \text{Baseline value}$.

This endpoint will use a CMH test stratified by the different levels of the randomization stratification factors of Baseline severity score (moderate, severe). The treatment group comparisons will be performed at Week 6 only, with descriptive statistics provided for each week. 95% CIs for the difference between 2 proportions will be calculated using the asymptotic Wald method.

7.6.2.3 Proportion of patients with $\geq 50\%$ reduction in pain intensity in ADPS based on Question 5 of ZBPI from Baseline to Week 6

Baseline and Week 6 ADPS scores will be based on the same mean values as derived for the primary endpoint. The frequency and percentage of patients with $\geq 50\%$ reduction in pain intensity from Baseline at Week 6 will be presented by treatment group. Response/Non-response categories will be defined as:

- If % change from Baseline $\leq (-50) \rightarrow$ Response
- If missing % change from Baseline or $> (-50) \rightarrow$ Non-response

Similarly, this endpoint will be analyzed as for 7.6.2.2.

7.6.2.4 Change from Baseline to Week 6 based on the Questions 9A-G of the ZBPI

The ZBPI is a patient-reported outcome (PRO) assessed on a validated electronic device completed at the time of the clinic visit. The ZBPI, a 9-item questionnaire assesses the severity of pain and its impact on functioning in patients with PHN.

The following pain interference categories based on Questions 9A-G of the ZBPI, completed at the time of the clinic visit, will be analyzed separately:

- General activity
- Mood
- Walking ability
- Normal work
- Relations with other people

- Sleep
- Enjoyment of life

The change from Baseline to Week 6 in pain interference will be summarized using standard descriptive statistics and the treatment effect will be evaluated using a similar MMRM method as specified for the primary efficacy analysis of change from Baseline to Week 6 in ADPS where the time point will be substituted by Visit instead of Week. The Baseline covariate included in the model is the Baseline value of the dependent variable under analysis.

7.6.2.5 Patient Global Impression of Change (PGIC) at Week 6

The PGIC, a 7-point rating scale, will assess the patient's belief about their overall improvement experienced at the end of treatment.

The frequency and percentages of patients within each category at Week 6 will be presented by treatment group. The treatment effect will be evaluated using an ANOVA model with treatment and randomization stratum of Baseline pain severity (moderate, severe) as independent variables. Least-square means of PGIC in each treatment group and the difference between LX9211 and placebo, along with their 95% CIs and p-value will be presented.

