6.1 Time Points and Visit Windows

Day 1, defined as the Baseline/Randomization visit, is also the first day that study treatment during the double-blind Treatment Period is planned to be started. Should study treatment start at a later date, Day 1 will be defined as the date that

CONFIDENTIAL

study treatment during the double-blind Treatment Period is initiated. Relative days after Day 1 are calculated as (assessment date – Day 1 date) + 1. Relative days prior to Day 1 are calculated as (assessment date – Day 1 date). The day prior to Day 1 is Day -1; there is no Day 0.

6.1.1 Primary efficacy, secondary efficacy, and other efficacy endpoints based on daily pain diary data

The following time point windows defined in [Table 1.1](#) will be used for the analyses of the primary efficacy endpoint, the secondary efficacy endpoints, and other efficacy endpoints based on the ADPS as well as for the secondary endpoint on pain interfering with sleep.

Table 1.1 Definition of time point windows for analyses based on ADPS and sleep interference rated each evening

Time point	Time point window ^a
Baseline	Day -7 to Day -1
Week 1	Days 1 to 7
Week 2	Days 8 to 14
Week 3	Days 15 to 21
Week 4	Days 22 to 28
Week 5	Days 29 to 35
Week 6	Days 36 to 42
Week 7	Days 43 to 49
Week 8	Days 50 to 56
Week 9	Days 57 to 63
Week 10	Days 64 to 70
Week 11	Days 71 to 77

^a relative to the date of first dose of study drug during the double-blind Treatment Period/ date of Randomization/date of Baseline Visit (Day 1)

The Baseline value for ADPS based on Question 5 of the ZBPI will be calculated as the mean value of the corresponding question over Week 2 of the single-blind Run-in Period, provided that ≥5 days with non-missing data from that period are available for analysis. The Baseline value for the interference with sleep using Question 9F of the ZBPI is defined as the value collected at the time of the clinic visit on Day 1 but prior to intake of the first dose of study drug. As a sensitivity analysis, the mean value of Question 9F of the ZBPI of daily diary over Week 2 of the single-blind Run-in Period will be used as the Baseline, provided that ≥5 days with non-missing data from that period are available for analysis.

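### Diary-rated sleep interference is measured against a single Day 1 clinic reading, while the like-for-like Run-in diary baseline is only a sensitivity analysis

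*SAP*

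**What the plan says.** SAP 7.6.2.1 builds the post-Baseline sleep score from the evening diary, as the "mean value of the Question 9F of the ZBPI, rated by patients each evening". It adds that "A minimum of 4 non-missing data within the target week period is required for the calculation". For the Baseline it takes one reading, which "is defined as the value collected at the time of the clinic visit on Day 1". SAP 6.1.1 gives the same definition in the text under Table 1.1 and adds a predose condition: "value collected at the time of the clinic visit on Day 1 but prior to intake of the first dose of study drug".

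Table 1.1 itself is titled "Definition of time point windows for analyses based on ADPS and sleep interference rated each evening", and its lead-in extends the windows to ADPS endpoints "as well as for the secondary endpoint on pain interfering with sleep". Its Baseline row is Day -7 to Day -1; Day 1 belongs to the Week 1 row.

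The diary-based alternative appears twice, both times as a sensitivity analysis. SAP 6.1.1 specifies the Run-in Week 2 diary mean of 9F with at least 5 days. SAP 7.6.3 plans a similar MMRM on the weekly sleep score: "The baseline is the Week 2 sleep score from the Run-in period". Separately, SAP 7.6.2.4 analyses the clinic-visit answers to Questions 9A-G, sleep included, by visit.

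**The concern.** The outcome averages 4 to 7 evening ratings made at home. The Baseline is one rating made at the clinic on a single day. A single day carries more day-to-day noise than a weekly mean, so it is a weaker covariate in the MMRM and leaves more residual variance in the treatment comparison.

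The same mismatch affects the within-arm changes. Any systematic difference between a clinic answer and an evening diary answer, or between Day 1 and the preceding week, would be counted as change from Baseline. SAP 7.6.1 reports within-arm changes with confidence intervals and p-values for the primary endpoint, and 7.6.2.1 borrows a similar method.

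The choice also departs from the primary endpoint, whose Baseline is the Run-in Week 2 diary mean. The SAP gives no reason for treating sleep differently, and the clinic reading already has a matching use in 7.6.2.4.

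**Working it through.** **Plan's own figure.** The documents give no SD, effect or power for sleep, so there is no figure to reproduce for this endpoint. The only stated power, 82.27% (SAP 2.3), belongs to the primary endpoint. A two-sample t-test with 37 per arm, difference 0.68, SD 1, 72 degrees of freedom and noncentrality 0.68 × √(37/2) = 2.92 returns 82.27%. It does not bear on the choice of baseline.

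**Definitions side by side.**
- Post-Baseline sleep: diary, weekly mean, at least 4 days (7.6.2.1).
- Main Baseline: clinic, one reading, Day 1 (6.1.1 text and 7.6.2.1).
- Baseline window in Table 1.1: Day -7 to Day -1.
- Sensitivity Baseline: diary, Run-in Week 2 mean, at least 5 days (6.1.1 and 7.6.3).

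Only the last agrees with both the outcome and the table.

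**Size of the precision loss.** Model a daily score as a week-level score plus independent day noise. Let r be the day-to-day ICC within a week, and c the correlation of week-level scores between Baseline and Week 6. Both are assumptions: r from 0.5 to 0.8, c from 0.4 to 0.8.

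- Reliability of a k-day mean: rel(k) = k·r / (1 + (k − 1)·r).
- Squared correlation of a k-day baseline with an m-day outcome: c²·rel(k)·rel(m). For a single day, rel(1) = r.
- Residual variance with the diary baseline, relative to the single reading: (1 − c²·rel(k)·rel(m)) / (1 − c²·r·rel(m)).

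Middle case, r = 0.7, c = 0.6, k = m = 7: rel(7) = 4.9/5.2 = 0.942. Numerator 1 − 0.36 × 0.942² = 0.680. Denominator 1 − 0.36 × 0.7 × 0.942 = 0.763. Ratio 0.892.

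| r | c | Baseline days | Outcome days | Ratio | Reduction |
|---|---|---|---|---|---|
| 0.8 | 0.4 | 7 | 7 | 0.8508/0.8764 = 0.971 | 3% |
| 0.7 | 0.6 | 7 | 7 | 0.6803/0.7625 = 0.892 | 11% |
| 0.5 | 0.8 | 7 | 7 | 0.5100/0.7200 = 0.708 | 29% |
| 0.7 | 0.6 | 5 | 7 | 0.6876/0.7625 = 0.902 | 10% |
| 0.5 | 0.8 | 5 | 7 | 0.5333/0.7200 = 0.741 | 26% |
| 0.7 | 0.6 | 5 | 4 | 0.7005/0.7724 = 0.907 | 9% |

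In the middle case 1/0.892 = 1.12, so the single-reading baseline would need about 12% more patients for equal precision on this endpoint: 74 × 1.12 ≈ 83.

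**Limits of the model.** Autocorrelated days make averaging less effective and shrink the gain. The pain-severity stratum, already in the MMRM, is ignored. The clinic reading is treated as equivalent to one diary day; if the change of setting weakens its correlation with the diary, the gain is larger.

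**Are the Run-in 9F data there?** Protocol 5.1.2 and SAP 2.2 name only Question 5 for the Run-in evening diary. Evening rating of 9F is first named for the double-blind period (protocol 5.1.3). The schedule of events mentions other ePRO questions on the e-diary, but its timing bar is not readable in the available copy. Run-in collection of 9F therefore rests on the two SAP sensitivity-analysis statements.

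**The case against.** The matched analysis is prespecified, so both results will be available and the question is only which one is labelled main. The endpoint is exploratory and unadjusted (SAP 7.6), and the trial is sized on the primary endpoint alone. The Day 1 clinic ZBPI is clearly scheduled, whereas Run-in 9F collection is not confirmed. The precision figures use assumed inputs and run from negligible to notable. The clinic and diary use the same item, the same 0-10 scale and the same 24-hour recall, and both are electronic self-report, so a shift between settings is possible but not shown. All of this stands. It limits the weight of the point without giving a reason to prefer the less reliable Baseline.

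Three stronger readings are tempting and are not supported.

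- A reader might infer that the treatment comparison is biased. It is not: 6.1.1 requires the reading before the first dose, and the definition is identical in both randomized arms. The omission of the predose condition from 7.6.2.1 does not change that.
- A reader might infer that the SAP leaves a programmer unable to proceed. Table 1.1 does conflict with the text, but 6.1.1 and 7.6.2.1 agree on an explicit 9F definition, which settles what would be programmed. The Day -7 to Day -1 row also serves the sensitivity analysis.
- A reader might take the endpoint's place at the head of the list as a rank. It is list order only.

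**Conclusion.** The point holds as a moderate weakness in an exploratory secondary analysis. The main sleep analysis sets a single clinic reading against diary means, departs from the window that Table 1.1 states for this endpoint, and gives the better-matched Baseline the lesser role. The between-arm estimate remains unbiased.

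The cost is residual variance that the diary baseline would cut by about 3-29%, with 11% in the middle case. This assumes ICC 0.5-0.8, correlation 0.4-0.8, independent day noise and complete 7-day means. Within-arm changes are also harder to interpret, since they mix setting and averaging period with change over time.

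It would be too strong to say that the matched Baseline is already in hand; that depends on whether 9F was in the Run-in evening diary.

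**What to change.** Before unblinding, check the e-diary specification or the blinded data for evening 9F ratings in the Run-in.

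- **If collected:** in SAP 6.1.1 and 7.6.2.1, make the Day -7 to Day -1 diary mean of 9F (at least 5 days) the main Baseline, in line with Table 1.1. Keep the Day 1 clinic value as the sensitivity analysis, adjust 7.6.3 to match, and retain the clinic value as the Baseline for 7.6.2.4, where it fits.
- **If not collected:** correct Table 1.1 and its lead-in so that they do not imply a diary Baseline for sleep, and remove the sensitivity analysis from 6.1.1 and 7.6.3, since it cannot be run.

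The cost is one data check and a swap of two definitions. The small downside of the swap is losing any patient with fewer than 5 Run-in 9F entries. Randomization already requires at least 70% of second-week pain diary entries, which means 5 of 7 days (4/7 = 57%, 5/7 = 71%), so few should be lost if 9F is rated in the same evening sessions.
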